Investigators, statisticians, and clinical staff will be blinded to participant group assignments. The research coordinator, however, will be unblinded by necessity. Participants similarly must be unblinded to their incentive structure, however they will not be told the incentive structure of the other group, nor whether their group is designated the treatment or control group.

Implementation of this project will occur in four phases.

- Phase 1: Preparation. (Study Approval – July 2016). During this phase, a research coordinator will be hired, equipment will be purchased, and all systems will be tested to ensure basic functionality prior to recruitment of the first participant.
- Phase 2: Recruitment. (July 2016 – June 2017). This phase describes the up to 10 month recruitment period during which patients will be screened and enrolled on a rolling basis into the trial.
- Phase 3: Data acquisition. (Enrollment – 30 days post-operative). This phase, which will overlap with phase 2 and start at a different time for each participant, describes the period for each participant in which they are enrolled and actively encouraged to submit data via the Way to Health platform and via interviews by the research coordinator. This phase bounds the total time commitment for any single study participant.
- Phase 4: Optional additional data submission and final survey (31 days post-operative to 90 days post-operative). This phase describes a period where patients will be allowed to continue to access the Way to Health platform and submit data should they choose to do so. No financial rewards or active encouragement will take place during this time. A final survey will be administered at the conclusion of this 90 day period to capture mid-term outcomes and complications.
- Phase 5: Analysis and Publication (Enrollment completion – December 2017). Final analysis of all acquired data is projected to be complete and ready for submission for publication by the end of 2017.

METHODS:

1. Study Instruments:

- Beginning shortly before the planned surgery and continuing for 30 days after date of surgery, all participants will use Fitbit Zips to measure daily step counts. Patients will have the option of submitting up to 90 days of post-operative data. Post-operative ambulation has been repeatedly demonstrated to be beneficial to recovery by a number of different metrics, and the Zip device has been shown to be an accurate measure of step counts.^{4-10,31}

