Subjects will be assigned to groups using simple balanced randomization. Upon enrollment in Way To Health, patients will be automatically randomized into "financial incentives" and "control" arms by an off-site computerized randomization system which is part of the WTH platform.

4. Administration of Surveys and/or Process:

Step count data will be recorded and uploaded independently by participants after initial instruction by the research coordinator. Before and after hospitalization, the research coordinator will ensure that patients are successfully uploading data and will be available to address issues that arise.

Questionnaires will be administered via the Way To Health platform. At the specified time points in the study (initial enrollment, immediately prior to discharge from the hospital, 30 days post-operative, and 90 days post-operative) the patient will be prompted to log in to the platform and fill out the questionnaire. Responses will be automatically recorded to the secure database.

Patients will also be contacted by phone at 30 days and 90 days by the research coordinator to screen for complications that would not be present in the University of Pennsylvania Health System (UPHS) electronic medical record (EMR).

5. Data Management:

Data will be collected principally through the Way to Health platform, which is a web-based platform designed by the University of Pennsylvania Center for Health Incentives and Behavioral Economics specifically for the purpose of testing behavioral interventions such as ours in an academic research setting. This platform has already been used in a number of similar IRB-approved randomized trials at the University of Pennsylvania.

All data not stored on WTH will be stored on hospital or university-owned computers or on encrypted storage drives. Data access will be granted only as needed to a small number of researchers who have completed the appropriate training as mandated by the University of Pennsylvania.

Upon completion of the study, data collection sites will be taken down and data stores disconnected from live webservers. Data will be stored on research computers for a period of 5 years, after it will be stored entirely on encrypted archival drives if no follow-up projects have been initiated.

6. Subject Follow-up:

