3. If the patient is deemed eligible and has an upcoming PAT or stoma-marking appointment, the patient is met by the research coordinator after the appointment. Consent is obtained, preoperative questionnaires are administered (see schedule below), the patient is given the Fitbit device, the patient is registered with WTH, randomization occurs, and the patient is instructed on how to upload data. Data collection begins immediately and preoperative step counts are uploaded to the WTH website. Patients with ECOG performance status greater than or equal to 3 will be screened for by review of the medical record and by asking patients to select which of the first four statements in the performance status best describe them.
 - a. In the event that eligible patients are identified with no PAT or stoma-marking visit prior to surgery, the patient will be contacted by phone. Preliminary verbal consent will be obtained, questionnaires will be administered, the patient will be registered with WTH and randomized and the Fitbit device will be mailed to the patient's home. Consent is finalized in the preoperative holding area.
4. The research coordinator will monitor the data being uploaded to WTH and follow up as needed with the patient to ensure that he or she is able to begin tracking and uploading step counts.
5. Demographic information for the participant is abstracted from the medical record and recorded along with questionnaire and randomization arm in the study database.
6. On the morning of the first post-operative day, the research coordinator explains the financial reward scheme specific to the patient's randomization arm.
7. The initial \$25 compensation for participation will be written and sent upon submission of the patient's preoperative step data.
8. In the morning of each day of the hospitalization, the research coordinator assists the patient in uploading the previous day's step-count data to the Way to Health website. The website provides feedback and allocates financial rewards into a virtual wallet. During this time, the research coordinator will also assess for safety and burden on the patient as well as assisting the patient in making any preparations to transition data collection to the home setting.
9. On the day of discharge, the patient will be prompted to respond to a brief questionnaire addressing perceived barriers to ambulation in the hospital.

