10. After discharge, participants resume independently for uploading their daily step count data. The website continues to provide feedback with each upload and may be accessed *ad lib* should participants want to check their progress and rewards more frequently. Data collection continues through the 30th post-operative day.
11. On the 31st post-operative day, the WTH platform prompts the participant to fill out questionnaires according to the schedule below. On the business day following the 31st post-operative day, the research coordinator will also contact the patient to inquire about any hospitalizations, stays at skilled nursing facilities or rehab facilities, emergency room visits, or unplanned doctor visits occurred since discharge and relevant medical records will be obtained if these are not already available through the UPHS EMR. Contact information is updated as needed, and financial awards are mailed in the form of a bank check to the participant's preferred mailing address. The research coordinator will follow up with patients to ensure the questionnaires are completed.
12. Participants are allowed to continue collecting and uploading data through WTH for 90 days post-operatively, although no further financial incentives or monitoring by the research coordinator will be provided.
13. On the 91st post-operative day, the patient is prompted to fill out questionnaires according to the schedule below. This will include a brief section addressing continued personal use of the Fitbit or another personal activity tracking device. On the business day following the 90th post-operative day, the research coordinator contacts the participant by phone to screen for uncaptured complications.

The schedule for questionnaires will be as follows:

- Initial contact (PAT visit, stoma-marking visit, or phone): SHAQ20, IPAQ, MPPSS
- Day of discharge: barriers to ambulation in the hospital
- 30 day post-operative phone call: SHAQ20, IPAQ, MPPSS, screen for uncaptured complications
- 90 day post-operative phone call: SHAQ20, IPAQ, MPPSS, screen for uncaptured complications

2. Data Collection:

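### The unblinded research coordinator elicits the out-of-system events for the composite morbidity outcome, with no script and no arm-masked classification described

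*Combined protocol and SAP*

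**What the plan says.** **Who is blinded.** STUDY DESIGN states: "Investigators, statisticians, and clinical staff will be blinded to participant group assignments". It continues: "The research coordinator, however, will be unblinded by necessity". No other staff role is declared unblinded. On participants it says: "Participants similarly must be unblinded to their incentive structure", although they are not told the other group's scheme or which group is the control.

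**What the coordinator does.** Under STUDY PROCEDURES, 1. Detailed Description, step 6, on the first post-operative morning "the research coordinator explains the financial reward scheme specific to the patient's randomization arm". Under step 11, after day 30, "the research coordinator will also contact the patient to inquire about any hospitalizations", facility stays, emergency visits and unplanned doctor visits, with outside records obtained where the health system's record lacks them. Step 13 adds a day-90 phone screen. METHODS, 4. Administration of Surveys and/or Process, says the same: "Patients will also be contacted by phone at 30 days and 90 days by the research coordinator to screen for complications" that the local electronic record would not show.

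**What else feeds the outcome.** STUDY PROCEDURES, 2. Data Collection, has the electronic record reviewed for complications at the end of the study. It names neither the reviewer nor any masking. OBJECTIVES defines the composite as complications, unplanned readmissions or emergency department visits. STUDY PROCEDURES, 5. Statistical Analysis, compares these events between arms.

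**Mode of the functional questionnaire.** METHODS, 4 has questionnaires completed on the Way to Health platform. The schedule after step 13 instead lists "30 day post-operative phone call: SHAQ20, IPAQ, MPPSS, screen for uncaptured complications".

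**The concern.** An interviewer who knows the arm can, without intending to, probe harder or accept a vague answer more readily in one group. For events already in the health system's record this hardly matters, because the record review can find them. For events treated elsewhere, the conversation is the gateway: outside records can confirm an event that the patient reports, but no described step recovers one that was never elicited. What counts as a complication is also left undefined, which leaves room for judgement.

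At stake is the arm difference in the composite morbidity outcome. STUDY DESIGN and the Statistical Analysis section both say that the pilot's effect sizes are to inform larger trials of these same clinical outcomes.

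**Working it through.** **1. The passages side by side.**

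| Step in collecting composite events | Who, according to the plan | Blinded? |
|---|---|---|
| Explaining the arm-specific reward (step 6) | Coordinator | No |
| Eliciting out-of-system events, day 30 (step 11; METHODS, 4) | Coordinator | No |
| Eliciting out-of-system events, day 90 (step 13; METHODS, 4) | Coordinator | No |
| Obtaining outside records for reported events (step 11) | Not named | Not stated |
| End-of-study record review (Data Collection) | Not named | Not stated |
| Classifying events as composite events | Not described | Not stated |

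Phase 4 in STUDY DESIGN also mentions a final survey at 90 days to capture complications. The questionnaire schedule contains no instrument for this other than the phone screen, so it does not supply a separate, arm-independent route.

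**2. Size of a possible spurious difference.** The plan gives no figure to reproduce, so this is an illustration.

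- p, proportion of patients with a composite event: 30%, borrowed from the major-complication rate in BACKGROUND. The composite rate itself is not given. The 20% readmission rate is used as a second value.
- s, share of those patients whose event would be found only through the call: 10% to 50% (assumed).
- d, between-arm gap in the probability of eliciting such an event: 10 to 30 percentage points (assumed).

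Spurious difference = p × s × d.

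- p = 30%: 0.30 × 0.10 × 0.10 = 0.3 points, up to 0.30 × 0.50 × 0.30 = 4.5 points. Times 23 patients per arm, that is 0.07 to 1.03 patients.
- p = 20%: 0.20 × 0.10 × 0.10 = 0.2 points, up to 0.20 × 0.50 × 0.30 = 3.0 points.
- The result is proportional to p. Each further 10 points of event rate adds at most 0.10 × 0.50 × 0.30 = 1.5 points.

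**3. Against random error.** With the planned n = 46, so 23 per arm, SE = √(2p(1−p)/23).

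- p = 30%: √(0.42/23) = 13.5 points.
- p = 20%: √(0.32/23) = 11.8 points.

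Random error dominates in the pilot itself.

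**4. Carried into a later trial.** Suppose the true rates are 30% and 20% (assumed). At two-sided 5% and 80% power,

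n per arm = [1.96√(2p̄(1−p̄)) + 0.84√(p₁(1−p₁) + p₂(1−p₂))]² / (p₁−p₂)²,

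which gives 294 (with unrounded normal quantiles). At the extreme corner of the assumptions:

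- Under-elicitation only in the 20% arm: 20 − 3.0 = 17%. The pilot would show 30% against 17%, and n = 166 per arm.
- Under-elicitation only in the 30% arm: 30 − 4.5 = 25.5%. The pilot would show 25.5% against 20%, and n = 911 per arm.

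The documents do not indicate a direction, so neither case is a prediction.

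**The case against.** **The case for leaving the plan alone.** The calls supplement a record review. Step 11 already lists the event types to ask about, and outside records are sought. The plan openly says that the coordinator is unblinded and never promises blinded outcome assessment. The outcome is secondary, in a pilot declared not powered for group differences, and any plausible bias is about one patient per arm or less. Participants know their own incentives, so they could reveal them to any caller.

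**What stands.** All of this limits the size of the problem, and none of it closes the gap for events found only by the call. A list of event types is not a script with fixed probes. Unblinding is needed to explain the rewards; it is not needed to classify outcomes.

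**Stronger readings that the documents do not support.**

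- *The arm is stored with the morbidity data, so blinded staff can see it.* Step 5 has demographics "recorded along with questionnaire and randomization arm in the study database", but it sits between enrolment and the first post-operative day and does not mention morbidity data. Access is limited to need, and by privileges and passwords. Nothing shows that blinded staff see the arm.
- *The functional outcome is shown to be unprotected.* METHODS, 4 and steps 11 and 13 have the patient complete the questionnaires when prompted. The phone-call label in the schedule may only mark the time point. This is a conflict to reconcile.
- *The coordinator decides which events count.* The coordinator asks; no passage says who classifies. A bias estimate that assumes coordinator classification of all events has no footing.
- *The coordinator coaches patients, or mails the rewards.* The text describes help with uploads, a safety and burden check and preparation for home. The mailing has no named role.
- *Unplanned doctor visits enter the composite.* They are asked about, but are not a component.

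**Conclusion.** The point holds for the composite morbidity outcome only. As written, an unblinded interviewer is the one described route to out-of-system events, and blinding of the record review and of classification is unspecified (which is not the same as absent). Differential ascertainment is therefore possible; it is not demonstrated, and its direction is unknown.

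The range of 0.3 to 4.5 points rests wholly on the assumed s and d and on borrowing 30% as the event rate. It is small beside the pilot's sampling error. The reason to act is that, unlike sampling error, this bias would not shrink if a larger trial repeated the same procedure, and the pilot estimate is intended for planning. This is a cheap improvement to a secondary outcome, not a threat to the device-recorded primary outcome.

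**What to change.** 1. **Script the calls.** Use one fixed script for day 30 and day 90, with the same event questions and probes in both arms and a standard form. Keep the call separate from any discussion of rewards. This narrows the room for differential probing but does not blind the caller.
2. **Mask the classification.** Have an investigator, whom STUDY DESIGN already blinds, classify composite events from the electronic record, outside records and call forms with the arm removed. Complete this before the arm is linked for analysis, and write down beforehand what counts as a complication.
3. **Blinded caller, if feasible.** If a blinded member of the existing team is available, that person should make the calls, 46 × 2 = 92 at most. The resources section lists a resident physician but states neither availability nor blinding status, so this is optional.
4. **Reconcile the questionnaire mode.** Align METHODS, 4 with the schedule after step 13, so that the Stanford questionnaire is self-completed on Way to Health and not given by phone.

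**Cost.** Items 1, 2 and 4 need no new staff: a short script and form, one wording change, and a modest amount of investigator time to classify events for about 46 patients. A limit remains: participants may still reveal their incentives to a blinded caller, and what they report may itself depend on knowing them.

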Steps to Eliminate Postoperative Problems

v1.3 6/26/2016

PRINCIPAL INVESTIGATOR: [name] [name], MSCE (Co-PI), [name], MPH (Co-PI)

PROTOCOL TITLE: Steps to Eliminate Postoperative Problems

NCT02880176

INTRODUCTION AND PURPOSE:

Radical cystectomy with urinary diversion is associated with substantial perioperative morbidity, including deep venous thrombosis, prolonged ileus, and postoperative functional decline. Post-operative morbidity after cystectomy prolongs the length of stay, increases the risk of readmission, and adds substantially to health care costs. Protocols that emphasize early and frequent ambulation after surgery decrease post-operative morbidity, but poor patient adherence diminishes the effectiveness of these protocols, which are currently implemented only during the hospital stay. Financial incentives overcome present bias and offer a novel and practical approach to increasing ambulation during the post-operative period in the hospital and after discharge. In this application, we propose a pilot randomized, controlled trial to estimate the effect size of financial incentives on increasing post-operative ambulation in the hospital and post-discharge after radical cystectomy. Secondary outcomes include step count, composite morbidity, and functional decline. This proposal will provide the preliminary data needed to design future, larger trials that will test the effect of financial incentives to increase ambulation on post-operative complications, readmissions, and functional decline

OBJECTIVES:

In this study, we seek to determine whether financial incentives can be used as novel and practical approach to increase post-operative ambulation and thereby decrease post-operative morbidity. The primary outcome variable will be the percentage of the first 30 post-operative days on which study participants meet patient-specific ambulation goals. Secondary outcomes include 1) the number of steps taken per day, 2) composite morbidity outcome of complications, unplanned readmissions, or Emergency Department (ED) visits, and 3) functional decline as measured by the Stanford Health Assessment Questionnaire.

BACKGROUND:

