- The Stanford Health Assessment Questionnaire (SHAQ) is a broadly used and validated questionnaire which, in its shortened form, assesses subjects' ability to perform 20 different actions and the need for assistance with these actions. It also captures patients' global assessments of pain and well-being.³⁷ This will be administered preoperatively, 30 days post-operatively, and 90 days post-operatively to measured post-operative functional decline.
- The International Physical Activity Questionnaire (IPAQ) Short Seven Day form quantifies patient reported levels of physical activity over the seven days prior to the interview. It is similarly broadly used and has been previously validated against accelerometer data.³⁸ This will be administered preoperatively, 30 days post-operatively, and 90 days post-operatively to measure post-operative decline in physical activity and to discover differences in baseline physical activity that are not captured by preoperative step-count data.
- The Multidimensional Scale of Perceived Social Support (MPPSS) is a validated tool for assessing patient's self-assessed degree of support from others.³⁹ Prior research has suggested social support as an important factor in exercise behavior, which is consistent with our clinical observations.⁴⁰ This will be administered pre-operatively and a 30 and 90 days post-operatively to help account for confounding by this important and otherwise unmeasured variable.
- Barriers to ambulation in the hospital: Previous work has attempted to identify modifiable factors that prevent inpatient ambulation.⁴¹ Based on the factors identified in this study, we will ask participants to respond to a simple questionnaire consisting of a five-point Likert scale from "was a major barrier that prevented me from walking" to "was not a barrier that prevented me from walking". The prompts will be as follows: "Physical discomfort (e.g. pain, weakness, shortness of breath)", "Cumbersome medical devices (e.g. IVs, catheters, monitors)", "Fear of falling", "Lack of assistance from people", "Social discomfort/embarrassment", and "Lack of desire/motivation".

2. Group Modifications:

No modifications necessary.

3. Method for Assigning Subjects to Groups:

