Participants enrolled in the data-collection phase of the study will be required to upload step count data daily to the Way to Health Website. Upload rates will be monitored and participants who fail to upload data for 24 hours will be contacted via their preferred contact phone number listed in the electronic medical record. The research coordinator will attempt to reach the participant daily for 3 days by phone, email, and the MyPennMedicine secure messaging service. If there is no response, the participant will be considered to have declined further participation. A final attempt will be made to contact the participant for the study conclusion interview. Regardless of participation status at the study conclusion, a check for all earned funds will be mailed to the study participant at the conclusion of the 30 day trial period. If participants stop uploading data daily but it can be confirmed that they are continuing to use the Zip device, arrangements may be made to upload the data for the study period in batch within 10 days of the conclusion of the study and allocate financial rewards according to the data collected.

STUDY PROCEDURES:

1. Detailed Description:

Participants will be enrolled on a rolling basis as they are identified. The following describes the sequence of steps for each participant

1. A potential participant is scheduled for radical cystectomy by the clinical staff. The surgical case is entered into the University of Pennsylvania Health System's electronic medical record by a Division of Urology surgery scheduler.
2. The research coordinator, with the assistance of clinical staff, reviews the surgery schedule on a weekly basis to detect patients who have been scheduled for radical cystectomy. Clinical staff are asked to alert the research coordinator if a patient is scheduled for cystectomy with a short lead time prior to the procedure. When a new case is scheduled, the coordinator reviews the patient's chart for eligibility.

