This study does not involve the analysis of existing data, blood, or tissue specimens. It will involve review of the patient's University of Pennsylvania Health System electronic medical record at several points in the study. After the patient is scheduled for cystectomy, the record will undergo screening for eligibility. No data will be abstracted from the record at this point. After enrollment the chart will be reviewed again for demographic information and past medical history which will be abstracted into the research database. It may also be reviewed as necessary during the course of the study to ensure ongoing safety of participants. Finally, the record will be reviewed at the conclusion of the study to assess for complications. In the case of missing or contradictory data, the electronic medical record may be referenced to ensure the quality of collected data after the end of the study, but these reviews shall not substantially expand the scope of the data collected beyond demographic information, vitals, and past medical history present at time of study initiation.

3. Genetic Testing:

Not applicable

4. Use of Deception:

Not applicable.

5. Statistical Analysis:

We will use generalized estimating equations with participant random effects and fixed effects for time to determine the association between financial incentives and 1) achieving step goals, 2) mean number of steps taken, 3) complications, ED visits and hospital readmissions, and 4) functional decline.

As a pilot study, the proposed research will provide preliminary data (e.g. effect sizes, feasibility) needed to design larger trials that will determine the effectiveness of financial incentives to increase ambulation on decreasing post-operative complications, readmissions, and functional decline. This study was therefore not powered to detect a statistically significant difference between the groups.

RISK/BENEFIT ASSESSMENT:

1. Risks:

The primary risk is that the interventions taken in this trial result in behavioral changes that are actually deleterious to patient recovery. In theory, increased ambulation may lead to increased falls, increased pain, herniation or other wound

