- Whenever feasible, identifiers will be removed from study-related information.
- A Certificate of Confidentiality will be obtained, because the research could place the subject at risk of criminal or civil liability or cause damage to the subject's financial standing, employability, or liability.
- A waiver of documentation of consent is being requested, because the only link between the subject and the study would be the consent document and the primary risk is a breach of confidentiality. (This is not an option for FDA-regulated research.)
- Precautions are in place to ensure the data is secure by using passwords and encryption, because the research involves web-based surveys.
- Audio and/or video recordings will be transcribed and then destroyed to eliminate audible identification of subjects.

5. Protected Health Information

The following elements of PHI will be explicitly recorded:

- Name
- Street address
- All elements of dates (except year) for dates directly related to an individual and all ages over 89
- Telephone numbers
- Electronic mail address
- Medical record number
- Device identifiers/serial numbers

6. Compensation:

All participants who enroll, complete the initial education, and provide a single day of step count data will keep their assigned Fitbit Zip device and will receive \$25 in cash on the second post-operative day. All participants who complete the study and have recorded step count data for at least 27 days (90%) will receive another \$75. Finally, participants who are randomized to the financial incentives arm will have the opportunity to earn an additional \$145 for meeting daily step goals (\$1.50/day plus a 1 in 5 chance at \$100). The final \$75 for study completion in addition to the earned financial rewards will be mailed as a check within 10 days of completion of the 30 day post-operative study period.

7. Data and Safety Monitoring:

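### The single analysis sentence names two incompatible models for four different outcomes and makes no use of the pre-operative SHAQ score and step count as covariates

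*Combined protocol and SAP*

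**What the plan says.** The protocol's STUDY PROCEDURES, 5. Statistical Analysis, contains the only statement of a model: "We will use generalized estimating equations with participant random effects and fixed effects for time to determine the association between financial incentives and" four outcomes, namely meeting step goals, mean steps, clinical events (complications, ED visits, readmissions) and functional decline. No section gives a link function, a working correlation or an effect measure. The same section says that the pilot is meant to supply effect sizes for larger trials and is not powered for a group comparison.

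The outcomes differ in structure:

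- **Primary (OBJECTIVES).** "The primary outcome variable will be the percentage of the first 30 post-operative days on which study participants meet patient-specific ambulation goals". The horizon is fixed.
- **Composite morbidity (OBJECTIVES).** No time window is given. Events are screened at both 30 and 90 days (METHODS, 4; STUDY PROCEDURES, 1), for example "90 day post-operative phone call: SHAQ20, IPAQ, MPPSS, screen for uncaptured complications".
- **SHAQ (METHODS, 1. Study Instruments).** "This will be administered preoperatively, 30 days post-operatively, and 90 days post-operatively to measured post-operative functional decline". Nothing says how the pre-operative score enters the analysis.
- **Steps.** A pre-operative lead-in supplies a baseline count (STUDY DESIGN). It sets the goals but does not appear in the model.

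The protocol also expects some days without data. After three days of failed contact, "If there is no response, the participant will be considered to have declined further participation" (METHODS, 6. Subject Follow-up). The completion payment requires 27 recorded days, not 30 (RISK/BENEFIT ASSESSMENT, 6. Compensation).

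**The concern.** GEE estimates a population-averaged effect and handles repeated measures through a working correlation and a robust variance. Participant random effects define a mixed model, whose coefficients are conditional on the participant. An analyst must discard part of the sentence to run anything, and the plan does not say which part.

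For the composite the problem goes beyond labelling. With one yes/no per participant there is no repetition from which to estimate a participant effect and no variation in time.

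The sentence also leaves unused two baseline measurements that the trial already pays for. In a trial of about 46 people whose stated product is an effect size, the loss of precision is real. So is a later designer's uncertainty about which quantity a reported effect represents.

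**Working it through.** **The plan's own figure.** The analysis section contains no numerical assumption to reproduce. The only size is the projected 46 participants, put at half of those eligible. Half of 75 to 100 is 37.5 to 50, so 46 lies in range and would need 46/0.50 = 92 eligible patients. Equal arms give 46/2 = 23 each, which is used below.

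**1. Composite.** Suppose there is one binary record per participant over one window. A logistic model with a participant intercept then has one observation per intercept, so the intercept variance is not identified. Time takes a single value and is absorbed in the constant. Two of the sentence's three components (GEE clustering or random effect, and time) have nothing to act on. Two records per participant, at 30 and 90 days, would give time some content, but the plan does not describe that layout.

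**2. SHAQ and the pre-operative score.** Assume SD 1 at each visit and a common correlation r between any two of the three visits (r is not in the documents; 0.3, 0.5 and 0.7 are shown). The standard error of the arm difference is sqrt((2/23) × V), where:

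- day-30/90 average, change score: V = (1 + r)/2 + 1 − 2r
- day-30/90 average, adjusted for baseline: V = (1 + r)/2 − r²
- single visit, change score: V = 2(1 − r)
- single visit, adjusted for baseline: V = 1 − r²

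| | r = 0.3 | r = 0.5 | r = 0.7 |
|---|---|---|---|
| V, average, change | 1.05 | 0.75 | 0.45 |
| V, average, adjusted | 0.56 | 0.50 | 0.36 |
| SE, average, change | 0.302 | 0.255 | 0.198 |
| SE, average, adjusted | 0.221 | 0.209 | 0.177 |
| Variance ratio, average | 53% | 67% | 80% |
| SE, one visit, change | 0.349 | 0.295 | 0.228 |
| SE, one visit, adjusted | 0.281 | 0.255 | 0.211 |

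These formulas ignore the cost of estimating the baseline slope. In 10,000 simulated trials per correlation with 23 per arm, the adjusted average had empirical SD 0.222, 0.208 and 0.180, and both analyses were unbiased. The cost is therefore small.

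**3. Steps.** Let r be the correlation between the pre-operative count and a participant's mean post-operative count. Adjustment then multiplies the variance of the unadjusted arm difference by 1 − r²: 0.91, 0.75 and 0.51 at 0.3, 0.5 and 0.7.

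**4. Daily goals: when the model conflict changes the answer.** Fix the proportions of days at goal (assumed) and solve for the logistic random-intercept model that reproduces them, integrating over a normal intercept of assumed SD.

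- Marginal odds ratio, 50% versus 60%: (0.60/0.40)/(0.50/0.50) = 1.50. Conditional: 1.63, 1.95 and 2.41 at SD 1, 2 and 3.
- Marginal odds ratio, 70% versus 80%: (0.80/0.20)/(0.70/0.30) = 1.71. Conditional: 1.88, 2.33 and 3.02.

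On the percentage-point scale, with all 30 days recorded, both models give the same 10 points. The same holds for the difference in daily steps on an identity link.

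**5. Unrecorded days.** A participant at goal on 16 of 27 recorded days scores 16/27 = 59.3% if missing days leave the denominator and 16/30 = 53.3% if they count as not met. The outcome definition points to 30. A model fitted to daily records would by default use 27.

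**The case against.** The best reply is that this is an unpowered pilot with its primary outcome defined as a percentage. No odds ratio appears anywhere in the protocol, and any competent analyst would choose either GEE or a mixed model and report sensible results. Much of this stands. The odds-ratio contrast needs a logit link that the plan never names and intercept SDs that are assumed. Thirty days is the natural window for the composite, since the protocol says patients are followed for 30 days, although it never states this as the analysis window. Missing days are actively chased by contact after 24 hours, staff help in hospital and batch upload. A change score is unbiased under randomisation, so baseline adjustment is a matter of precision.

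Several stronger readings are tempting, and the documents do not support them:

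- **That the primary result is compromised.** With complete days the percentage-point difference does not depend on which model is kept.
- **That the two models diverge on the percentage-point scale once days are missing.** Such gaps come mainly from choosing an independence working correlation; GEE with an exchangeable correlation stays very close to the mixed model.
- **That the SHAQ effect is diluted by a pre-operative visit at which the incentive cannot act.** This requires the pre-operative score to be an outcome row, an unlikely reading when the outcome is decline.
- **That the model for daily steps is wrong.** Either model serves; only the baseline covariate is missing.
- **That false-positive rates are inflated.** Nothing in the documents establishes this, and no confirmatory test is planned.

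Pilot status does not dispose of the rest. The effect estimate and its precision are what the pilot is meant to deliver.

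**Conclusion.** The concern holds in limited form. The sentence joins two different models, and for a composite recorded once per participant its random and time effects cannot be estimated. It also omits adjustment for two baseline measures already collected. For SHAQ, adjustment brings the variance of the day-30/90 average to 53%, 67% or 80% of the change-score variance at correlations 0.3, 0.5 and 0.7, assuming 23 per arm and equal SDs and correlations across visits. The model conflict changes the reported effect only if daily goals are analysed on a logit link (1.50 against 1.63 to 2.41 in the 50% versus 60% case). The missing link, composite window and rule for unrecorded days are mostly absent detail. This should be fixed before analysis, but it does not threaten the trial's validity.

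**What to change.** Replace the sentence with one coherent model per outcome, dropping the random effects wherever GEE is kept.

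1. **Primary.** Share of post-operative days 1 to 30 at goal, reported as a percentage-point difference with 95% CI. State whether unrecorded days count as not met or leave the denominator, and report the other choice as a sensitivity analysis.
2. **Daily steps.** GEE or mixed model with arm and time, adjusted for the pre-operative step count.
3. **Composite.** One record per participant over a stated window; risk difference with 95% CI; no random or time effect.
4. **SHAQ.** Days 30 and 90 as outcomes, adjusted for the pre-operative score. Report the arm difference at each visit, because after day 30 "No financial rewards or active encouragement will take place during this time".

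A small-sample variance correction for any GEE is optional. The cost is one paragraph of wording and slightly more analysis code. Every measurement needed is already scheduled.
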